#### 5.2 Nivolumab

### 5.2.1 Characteristics, supply, packaging and labelling

Nivolumab is a programmed death receptor-1 (PD-1) blocking antibody marketed by Bristol-Myers Squibb Pharma EEIG. It will be supplied in 40 and/or 100 mg vials (10 mg/mL) in its commercial packaging with brand name "OPDIVO 10 mg/mL concentrate for solution for infusion" (pack size of one 10 mL vial (Type I glass) with a stopper (coated butyl rubber) and a flip-off seal (aluminium), and labelled appropriately as investigational material for this study. Nivolumab concentrate is a clear to opalescent, colourless to pale yellow liquid that may contain few light particles. (See also Summary of Product Characteristics (SmPC).

## 5.2.2 Transport of nivolumab

# 5.2.2.1 Interstate and International Transport

Nivolumab is shipped per manufacturer's instructions.

### 5.2.2.1.1 Drug Receipt and Approval of Shipment

The supply of nivolumab is managed by Transgene based on nivolumab inventory of sites and patient's treatment prospects.

Detailed information on nivolumab receipt instructions and approval of shipment process is provided in the Product Handling Manual.

# 5.2.2.2 Transport within the Institution

No specific instructions.

#### 5.2.3 Conditions of storage and use

In accordance with its USPI/ EU SmPC, nivolumab vials must be stored in the refrigerator at 2-8°C in the original package in order to protect from light.

From a microbiological point of view, once opened, nivolumab should be used immediately. If not used immediately, nivolumab infusions should be stored at room temperature (20-25°C) and room light for no more than 4 hours from time of preparation. This includes room temperature storage of infusion in IV container and time for administration of infusion. Alternatively, nivolumab infusion can be stored under refrigeration at 2 to 8°C (36-46°F) for no more than 24 hours from the time of infusion preparation and protected from light. The infusion should not be frozen.

## 5.2.4 Preparation for administration

Preparation of nivolumab should be performed by trained personnel in accordance with USPI/EU SmPC and good practices rules, especially with respect to asepsis.

The required volume of nivolumab should be withdrawn using an appropriate sterile syringe and transferred into a sterile, evacuated glass bottle or an intravenous container (PVC or

polyolefin). Nivolumab should be used directly or be diluted with either 9 mg/mL (0.9%) sodium chloride solution for injection, USP or 50 mg/mL (5%) glucose solution for injection, USP, to prepare an infusion with a final concentration ranging from 1 mg/mL to 10 mg/mL. Diluted solution should be mixed by gentle inversion, but should not be shaken. Partially used or empty vials of nivolumab should be discarded.

#### 5.2.5 Unused nivolumab destruction or return

Any unused portion of the infusion solution must not be stored for reused. Any unused nivolumab or waste material will be disposed of in accordance with local requirements. A certificate of destruction will be completed and provided to Transgene (copy retained by the site).

Alternatively, unused nivolumab may be returned to the IMP supply provider contracted by Transgene with the appropriate documentation. A certificate of return will be completed and provided to the drug supply provider (copy retained by the site).

# 5.2.6 Nivolumab accountability

Nivolumab will only be dispensed, according to the Investigator's prescription, to patients who meet all selection criteria. The Investigator/Pharmacist, or delegated person, will maintain a nivolumab accountability log detailing the dates and quantities dispensed for each patient along with kit numbers.

Nivolumab accountability records will be verified by the monitor during site visits.

All documentation related to nivolumab shipment, receipt, dispensing, destruction, temperature monitoring, etc., must be filed in the Pharmacy file and must be available for monitor verification, audit and inspection. A copy of all drug accountability records will be returned to Transgene at the end of the study.

#### 6 TREATMENT PLAN

#### 6.1 Treatment administered

### 6.1.1 Treatment regimens

### 6.1.1.1 Phase I part:

Safety and efficacy will be assessed in 6 patients, using a standard regimen for dose level 1 as 3 bi-weekly IT injections of 1x10^9 pfu for Pexa-Vec and 240 mg IV q2weeks for nivolumab (Figure 1: IMP administration scheme).

In case of a Dose-Limiting Toxicity (DLT) is observed in more than one patient out of the first 6 patients, or in the occurrence of a landmark AE, one de-escalation regimen is planned:

• Dose level -1: 3 bi-weekly IT injections of 3x10^8 pfu for Pexa-Vec and 240 mg q2weeks for nivolumab OR 3 bi-weekly IT injections of 10^9 pfu for Pexa-Vec and 240 mg q3 weeks for nivolumab, depending on the DLT profile relative to the known toxicity of each component of the combination, as judged by the Independent Safety Committee (ISC).

A landmark AE is an anticipated effect of the combination, defined as either increase in severity of hepatic cytolysis (doubling of AST – ALT baseline blood concentrations), or significant deterioration of hepatic function (INR, bilirubin), or increase in number or severity of immunerelated AEs, or increase in number or severity of Pexa-Vec-related skin lesions.

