- In the Phase I part, **Dose-Limiting Toxicities (DLTs)** are defined as the occurrence of any of the following events evaluated as related to study drugs and occurring during the first 4 weeks (up to D29), which is defined as the DLT period:
- 1. All Grade 3-4 non-hematologic toxicity that represents a 2-grade increase over baseline, excluding:
  - Untreated or inadequately treated nausea, vomiting and diarrhea,
  - Untreated or inadequately treated fever > 40.0°C lasting less than 24 hours (Grade 3); only fever > 40.0°C lasting more than 24 hours (Grade 4) qualifies for DLT,
  - Alopecia,
  - Grade 3 fatigue that returns to grade 2 or less within 7 days,
  - Grade 3 laboratory/metabolic abnormalities, other than ALT or AST, that are not considered clinically significant and that return to grade 2 or less within 72 hours.
- 2. Any Grade ≥ 3 treatment-related acute immune-related AE involving major organs, such as: immune-related pneumonitis, colitis, nephritis, hepatitis, endocrinopathies, immune-related rash and other rare but severe immune-related reactions.
- 3. Grade  $\geq$  3 injection site reaction.
- 4. AST or ALT  $\geq$  10xULN, even if asymptomatic, unless it is related to a definite progression of liver metastases or another clearly identifiable etiology; doubling of AST or ALT that is concurrent with a doubling of the total bilirubin.
- 5. Any toxicity at least possibly related to study therapy that results in a delay in treatment of 2 or more weeks.

[figure not shown]
IMP1 (Investigational Medicinal Product): Nivolumab, programmed

IMP2: Pexastimogene devacirepveo, Vaccinia GMCSF / Elivoridine

Clinical Protocol: 1 G0006.01

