# 6.2 Recommended Phase II dose (RP2D)

In the Phase I part, all patients will be monitored up to D29 for the occurrence of DLTs that defines the DLT period. The RP2D is defined as the maximum dose level (1 or -1) at which a DLT attributable to the IMPs is observed at most in one patient out of 6 patients in the DLT period and upon final recommendation of the ISC that will prevail.

The **DLTs**, applicable for the Phase I part of the study, are defined as such:

- 1. All Grade 3-4 non-hematologic toxicity that represents a 2-grade increase over baseline, excluding:
  - Untreated or inadequately treated nausea, vomiting and diarrhea,
  - Untreated or inadequately treated fever > 40.0°C lasting less than 24 hours (Grade 3); only fever > 40.0°C lasting more than 24 hours (Grade 4) qualifies for DLT,
  - Alopecia,
  - Grade 3 fatigue that returns to grade 2 or less within 7 days,
  - Grade 3 laboratory/metabolic abnormalities, other than ALT or AST, that are not considered clinically significant and that return to grade 2 or less within 72 hours.
- 2. Any Grade ≥ 3 treatment-related acute immune-related AE involving major organs, such as: immune-related pneumonitis, colitis, nephritis, hepatitis, endocrinopathies, immune-related rash and other rare but severe immune-related reactions.
- 3. Grade  $\geq$  3 injection site reaction.
- 4. AST or ALT  $\geq$  10xULN, even if asymptomatic, unless it is related to a definite progression of liver metastases or another clearly identifiable etiology; doubling of AST or ALT that is concurrent with a doubling of the total bilirubin.
- 5. Any toxicity at least possibly related to study therapy that results in a delay in treatment of 2 or more weeks.
- 6. Hematological:
  - Grade ≥ 3 or ≥ 2-grade increase over baseline of neutropenia lasting for more than 7 days.
  - Neutropenic fever.
  - Grade 4 thrombocytopenia or grade 3 thrombocytopenia with clinically significant bleeding.
- 7. Cardiac: association of the 3 following cardiac abnormalities
  - Left ventricular ejection fraction (LVEF) less than the lower limit of normal (LLN), as
    assessed by echocardiography and symptomatic due to drop in ejection fraction,
    responsive to intervention,
  - Increase of blood troponin T or I above the upper limit of normal (ULN),
  - Any ECG abnormality consistent with a Grade 3 cardiac disorder.

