- Dose-limiting toxicity (DLT): Any of the following treatment-related adverse events (AEs) and is evaluated and reported from Baseline through Day 29 in the Phase I section of the study; grades are referring to NCI CTCAE v. 4.03:
  - 1. All Grade 3-4 non-hematologic toxicity that represent a 2 grade increase over baseline, excluding:
    - Untreated or inadequately treated nausea, vomiting and diarrhea,
    - Untreated or inadequately treated fever > 40.0°C lasting less than 24 hours (Grade 3); only fever > 40.0°C lasting more than 24 hours (Grade 4) qualifies for DLT,
    - Alopecia,
    - Grade 3 fatigue that returns to grade 2 or less within 7 days,
    - Grade 3 laboratory/metabolic abnormalities, other than ALT or AST, that are not considered clinically significant and that return to grade 2 or less within 72 hours.
  - 2. Any Grade ≥ 3 treatment-related acute immune-related AE involving major organs, such as: immune-related pneumonitis, colitis, nephritis, hepatitis, endocrinopathies, immune-related rash and other rare but severe immune-related reactions.
  - 3. Grade  $\geq$  3 injection site reaction.

- 4. AST or ALT  $\geq$  10xULN, even if asymptomatic, unless it is related to a definite progression of liver metastases or another clearly identifiable etiology; doubling of AST or ALT that is concurrent with a doubling of the total bilirubin.
- 5. Any toxicity at least possibly related to study therapy that results in a delay in treatment of 2 or more weeks.
- 6. Hematological:
  - Grade  $\geq 3$  or  $\geq 2$ -grade increase over baseline of neutropenia lasting for more than 7 days.
  - Neutropenic fever.
  - Grade 4 thrombocytopenia or grade 3 thrombocytopenia with clinically significant bleeding.
- 7. Cardiac: association of the 3 following cardiac abnormalities
  - Left ventricular ejection fraction (LVEF) less than the lower limit of normal (LLN), as assessed by echocardiography and symptomatic due to drop in ejection fraction, responsive to intervention,
  - Increase of blood troponin T or I above the upper limit of normal (ULN),
  - Any ECG abnormality consistent with a Grade 3 cardiac disorder.

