- DLT Period: The DLT period is the period during which the DLTs are recorded in a patient eligible for safety assessment within the Phase I section of the study, defined as the interval between the 1st Pexa-Vec administration (Day 1) and 3rd Pexa-Vec administration concomitant to the 2nd nivolumab infusion (Day 29 in evaluable patients, who have received all three Pexa-Vec IT injections and 2 nivolumab IV infusions in Phase I). In the event that a patient does not complete the DLT period and withdraws for other reasons than toxicity, then the patient will not be considered evaluable for Phase I and will have to be replaced.

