## Intent to treat population

In addition, there will be intent to treat population, i.e. on all patients treated with at least one administration of either drugs, irrespective of the time of stopping the treatment. The patients will be included according to the treatment planned and this dataset will be used for efficacy evaluation.

A patient evaluable for Phase I assessments is an eligible patient, who completed the DLT period up to D29, including all three intratumoral injections of Pexa-vec and two infusions of nivolumab. A patient evaluable for Phase IIa assessments is an eligible patient having received at least 2 administrations of Pexa-Vec and 2 administrations of nivolumab and undertaken at least one post-baseline radiological assessment or exhibited any evidence of disease progression other than radiological. Per protocol analysis for the Phase I section should include at least 6 evaluable patients treated with the same dose level; per protocol analysis for the Phase IIa section should include at least 30 evaluable patients that may include comparable Phase I patients (population, regimen), who are evaluable for Phase IIa analysis.

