#### 8.8.1 Adverse Events

#### 8.8.1.1 Definitions

From the date of signature of ICF and up to first IMP administration (i.e. before the patient receives any IMP) only SARs caused by a protocol-required procedure (e.g., related to invasive procedures such as blood sampling) will be collected and reported. AEs, SAEs, or procedure related ARs that occur during this period, and that are considered by the investigator as relevant to the patient condition, will be collected as a current medical history.

After the initiation of either IMP and up to 28 days after the last dose of IMP, all AEs and SAEs will be collected and recorded on the eCRF. SAEs will also be reported to Transgene.

SAEs occurring more than 28 days after the last dose of IMP, and evaluated by the Investigator as related to the IMP will be collected and reported to Transgene indefinitely even after end of study. Only SAEs occurring prior to end of study will be reported in the eCRF.

All AEs will be coded using the Medical Dictionary for Regulatory Activities (MedDRA) central coding dictionary using latest version available. NCI-CTCAE version 4.03, dated June 14, 2010 will be used.

All AEs will be reported on the "Adverse Event" section of eCRF.

Dose-limiting toxicity (DLT) is defined as any of the following treatment-related adverse events (AEs) and occurring during the first 4 weeks (up to D29), in the Phase I part of the study; grades are referring to NCI CTCAE v. 4.03:

- 1. All Grade 3-4 non-hematologic toxicity that represent a 2-grade increase over baseline, excluding:
  - Untreated or inadequately treated nausea, vomiting and diarrhea,
  - Untreated or inadequately treated fever > 40.0°C lasting less than 24 hours (Grade
     3); only fever > 40.0°C lasting more than 24 hours (Grade 4) qualifies for DLT
  - Alopecia,
  - Grade 3 fatigue that returns to grade 2 or less within 7 days.
  - Grade 3 laboratory/metabolic abnormalities, other than ALT or AST, that are not considered clinically significant and that return to grade 2 or less within 72 hours.
- 2. Any Grade ≥ 3 treatment-related acute immune-related AE involving major organs, such as: immune-related pneumonitis, colitis, nephritis, hepatitis, endocrinopathies, immune-related rash and other rare but severe immune-related reactions.

- 3. Grade  $\geq$  3 injection site reaction.

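### On the three-weekly nivolumab option of dose level -1, the second infusion (D36) falls after the fixed D29 DLT cut-off, so the Phase I evaluability and DLT-period definitions cannot be met as written

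*Protocol*

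**What the plan says.** Protocol 6.1.1.1 offers two versions of dose level -1. One lowers Pexa-Vec to 3x10^8 pfu and keeps nivolumab every 2 weeks. The other keeps three bi-weekly Pexa-Vec injections at 10^9 pfu and gives "240 mg q3 weeks for nivolumab, depending on the DLT profile relative to the known toxicity of each component of the combination". The ISC chooses between them. Protocol 6.1.2.2 starts nivolumab on D15, and no other start day is given for dose level -1.

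The DLT cut-off is the same wherever it is stated:

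- Protocol Synopsis, safety assessments: "occurring during the first 4 weeks (up to D29), which is defined as the DLT period".
- Protocol 6.2: "In the Phase I part, all patients will be monitored up to D29 for the occurrence of DLTs that defines the DLT period".
- Protocol 10.1: "evaluated and reported from Baseline through Day 29 in the Phase I section of the study".
- SAP 8.8.1.1: "occurring during the first 4 weeks (up to D29), in the Phase I part of the study".

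Protocol 6.2 applies one criterion to both levels. The recommended Phase II dose is the "maximum dose level (1 or -1) at which a DLT attributable to the IMPs is observed at most in one patient" out of six, within the DLT period and subject to the ISC's final recommendation.

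Two definitions put both nivolumab infusions inside that period. Protocol 10.1 ends the DLT period at the third Pexa-Vec injection, given together with the second nivolumab infusion, and equates this with "Day 29 in evaluable patients, who have received all three Pexa-Vec IT injections and 2 nivolumab IV infusions in Phase I". Protocol 12.6 defines a patient evaluable for Phase I as one "who completed the DLT period up to D29, including all three intratumoral injections of Pexa-vec and two infusions of nivolumab". SAP 7.2 has the ISC review safety when six evaluable patients have reached their Day 29 visit. Neither document gives the three-weekly option a window of its own.

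**The concern.** The D29 language fits a two-weekly schedule, where the second infusion and the end of the DLT period fall on the same day. On the three-weekly option they do not, and the plan does not adapt.

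Two things are at stake. First, a rule that governs a safety decision cannot be followed as written: a patient without a DLT has had one infusion by D29, not two. Secondly, if the definitions are read loosely so that the cohort can be completed, the DLT count is still taken before the second infusion. This option would be chosen because the DLT profile at dose level 1 pointed to nivolumab. Its DLT criterion would then be read from days on which the schedule has not yet departed from the one that failed.

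**Working it through.** **Inputs.** First nivolumab infusion D15; windows of ±1 day for cycles 1 to 3 (Protocol 6.1.2.2). Interval 14 days at dose level 1 and 21 days on the option. Pexa-Vec on D1, D15 and D29 in both (Protocol 6.1.2.1). Day 29 visit ±1 day (Protocol 8.6). Two weeks between consecutive enrolments in Phase I (Protocol 6.3.1).

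**Step 1: reproduce the plan's own day.** Infusion k falls on D15 + interval × (k − 1). At dose level 1, 15 + 14 = D29, which matches Protocol 8.6.

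**Step 2: the three-weekly option.** 15 + 21 = D36. Earliest: 14 + 21 − 1 = D34. Latest: 16 + 21 + 1 = D38. The gap from the Day 29 visit (D28 to D30) is nominally 36 − 29 = 7 days, at least 34 − 30 = 4 and at most 38 − 28 = 10. No use of the visit windows brings the second infusion inside the DLT period.

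**Step 3: scheduled cumulative nivolumab.**

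| Days | Dose level 1 | Three-weekly option |
|---|---|---|
| D15 to D28 | 240 mg | 240 mg |
| D29 to D35 | 480 mg | 240 mg |
| D36 to D42 | 480 mg | 480 mg |
| D43 to D56 | 720 mg | 480 mg |

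Pexa-Vec is the same in both columns. Scheduled exposure therefore matches on D1 to D28, which is 28 of the 29 days in the DLT window. The one difference is the nivolumab infusion not given on D29, the last day.

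**Step 4: apply the definitions to a DLT-free patient on this option.**

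- *Strict reading (Protocol 10.1 and 12.6).* Two infusions are needed by D29 and one has been given, so the patient is not evaluable. Protocol 6.6.2 then calls for a replacement, who meets the same obstacle. The third Pexa-Vec injection (D29) and second nivolumab infusion (D36), which Protocol 10.1 treats as one occasion, are 7 days apart.
- *Lenient reading (Protocol 6.6.2, SAP 2.3 and 6.1).* Two infusions and a completed DLT period are both required, but not expressly by the same date, so evaluability can mature at D36. The DLT count still closes at D29. An event on D30 to D36 that meets the DLT criteria is not counted, and that interval includes the day of the second infusion. At dose level 1, the day of the second infusion is counted.

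**Step 5: effect on timing under the lenient reading.** When patient 6 reaches D29, patient 5 is at least at 29 + 14 = D43, past D38. Five of six patients are then due to have had the second infusion. The ISC review waits for one patient, for about 7 days.

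**The case against.** The ISC does not decide on DLTs alone. Protocol 3.1.1 has it analyse all Phase I safety results, and Protocol 6.1.1.2 and 6.2 let its recommendation prevail. Phase IIa also requires that no landmark AE has occurred, including more frequent or more severe immune-related AEs, and no D29 limit is set on that condition. With the two-week stagger, when patient 6 is at D29 patients 5, 4, 3 and 2 are at about D43, D57, D71 and D85 or later, and patient 1 is further on. All of this stands. A reader might infer that the regimen would be cleared on D1 to D28 data alone; the documents do not support that.

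A reader might also infer that the cohort could never be completed. That holds only under the strict reading. Protocol 6.6.2, SAP 2.3 and SAP 6.1 leave room for evaluability to mature at D36, with a wait of about a week.

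A third inference is that moving the cut-off to D36 would turn the criterion into a test of the lower frequency. It would not. Dose level 1 is not scored for DLTs after D29, so the added days have no scored comparator. Most of the longer window still follows a single infusion, and cumulative dose differs again from D43. The at-most-one-in-six rule is an absolute threshold, not a comparison between levels.

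Finally, the situation is contingent and may have passed. Protocol 3.1.3 expected Phase I recruitment to finish by January 2018; the protocol version is dated March 2019 and the SAP December 2018. The Phase I outcome is not reported in either. This lowers the priority, but the option is still in the current text and its definitions still conflict.

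**Conclusion.** The point holds as a defect in the stated rule, of low priority. On the three-weekly option the second infusion is due on D36 (D34 to D38), while the DLT period closes at D29 for every Phase I patient. Read strictly, the two-infusions-by-D29 definitions cannot be met without a DLT. Read leniently, the cohort can be completed, but the DLT criterion covers one infusion instead of two, over exposure scheduled identically to dose level 1 until D28, and leaves out D30 to D36.

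This assumes that dose level -1 keeps the D15 start. The text gives no other day, and Figure 1 was not available in readable form. The stagger argument assumes that the Phase I two-week interval also applies to the second cohort. The problem arises only if dose level 1 fails and the ISC picks this option. Dose level 1 and the 3x10^8 pfu two-weekly option are unaffected.

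**What to change.** For the three-weekly option only, define the DLT period as running from D1 to no earlier than the day of the second nivolumab infusion, nominally D36. Align Phase I evaluability, the DLT population and the ISC trigger in SAP 7.2 with that day. Dose level 1 and the 3x10^8 pfu option keep D29.

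The wording to revise is in the Protocol Synopsis (DLT definition), the Definitions table (evaluable patient), Protocol 6.2, 6.6.2, 10.1 and 12.6, and SAP 2.3, 6.1, 7.2 and 8.8.1.1. If the first-patient hold to D29 (Protocol 3.1.1 and 6.3.1) is meant to apply to this cohort, it needs the same adjustment.

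This makes the rule satisfiable and gives the two-infusion coverage that dose level 1 has, where the period also ends on the day of the second infusion. It should not be presented as evidence on whether three-weekly dosing is safer. Following patients for a full interval after the second infusion, to 36 + 21 = D57, is optional.

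The cost is protocol and SAP wording, plus about one week's later readout for that cohort if the option is used.
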